7.5.1.2 Cone spacing

The analytic template in §7.5.1.1 (and in §7.5.1.3 below) will be applied to the cone spacing measurements. Inferentially, we consider cone spacing as a secondary outcome.

7.5.1.3 Longitudinal analysis

As a complement to the above analysis, we will also model the clinical trial data using linear mixed models (e.g. Yasui et al, 2004), a modeling approach we have used in analysis of cone spacing and density data in the pilot study (Talcott et al., 2011)—provided interim observations are available.

7.5.1.4 Image grading

The outcome variables above will be derived by averaging cone spacing and cone density measurements for independent graders. These graders will be masked to the treatment during the entire trial.

The linear mixed model framework may be expanded to model the ratings individually by including a rater-specific random effect.

7.5.2 Secondary efficacy variables

The following methods will be used to assess secondary endpoints, as indicated. While we will report Holm-corrected p-values (correcting for six hypothesis tests), we note that such procedures are conservative and reduce our power to detect lack of safety. We emphasize that safety cannot be assessed by means of these hypothesis tests, that alternative lower bounds may be of interest to the SMC, and that a full assessment must take into account multiple factors and clinical judgment. As with the primary outcome variable, the analytic results in this section are relevant both to safety (when results are worse in the treated eye), and to efficacy (when the results are better).

7.5.2.1 Visual acuity

The template of §7.5.1.1 will be used here, except that we will simply model the difference in visual acuity between the eyes (regions of interest play no role, and we do not have multiple graders). We will test the hypothesis that the difference in visual acuity between the treatment and control eyes is constant in time, using a two-sided alpha of 0.05 (following Holm correction). Models including the covariates (such as age and diagnosis) will be explored.

7.5.2.2 Visual field sensitivity

As above, we will follow the template in §7.5.1.1, using visual field sensitivity in each quadrant to produce an overall measure for each eye. A two-sided alpha of 0.05 will be used (following Holm correction).

7.5.2.3 Foveal sensitivity

Foveal sensitivity will be examined in the same way as visual acuity (one measurement per eye), using the same strategy as in §7.5.2.1. A two-sided alpha of 0.05 will be used (following Holm correction).

7.5.2.4 Outer nuclear layer

Outer nuclear layer measurements will also be examined in the same way as visual acuity (one measurement per eye), using the same strategy as in §7.5.2.1. A two-sided alpha of 0.05 will be used (following Holm correction).

7.5.2.5 Outer segment thickness

Outer segment thickness will also be examined in the same way as visual acuity (one measurement per eye), using the same strategy as in §7.5.2.1. A two-sided alpha of 0.05 will be used (following Holm correction).

7.5.2.6 ERG measurements

We will model photopic b-wave measurements at the baseline, 12, 24, and 36 month times using the template of §7.5.1.1. This will be conducted at a two sided alpha of 0.05 (following Holm correction for multiple comparisons). Scotopic b-wave, as well as photopic and scotopic a-wave

measurements, will be reported descriptively and will provide additional information which can guide assessments of safety.

7.5.2.7 Other outcomes

For the incidence of adverse events following application of the investigational product in all subjects, we propose to use Poisson or negative binomial random-effects regression (extending to a more general hidden Markov model in the event of poor fit of the simpler models). Specifically, we will test the hypothesis that the underlying event rate per unit time is the same in the treatment and sham eyes. As a secondary analysis, we will analyze the time to first adverse event in each group using Cox proportional hazards regression (using baseline medical history as well as time since last treatment as covariates). We emphasize that while the statistical fit may be informative, decisions about drug safety (or trial continuation) will not be based solely on statistical criteria.

7.5.2.8 Other analyses

We will also explore multivariate models (using many variables as outcomes), and explore the correlation structure between these variables cross-sectionally and longitudinally.

Plots of the average cone spacing in the treatment eye as a function of average cone spacing in the treatment eye will also be examined, adjusting for mean distance to the fovea (and likewise for density, and all other ocular measurements). Exploratory models in which the spacing in the control eye is used as a predictor of the spacing in the treatment eye may be examined to provide additional statistical insight, but not as formal hypothesis tests.

7.6 Additional statistical considerations

7.6.1 Software

The standard software package R version 2.11 or later (<http://www.r-project.org>) for the MacIntosh OS X will be used for all descriptive and inferential analyses. SAS PROC MIXED (SAS Institute, Cary, North Carolina, USA) will be used in addition to R for fitting linear mixed models.

7.6.2 Missing data and loss to follow-up

Missing values of cone spacing or density will be handled by regression-based multiple imputation in several steps.

- Missing values for one grader at a baseline visit, when observations at the same visit are available from the other grader
- Missing values for both graders at a baseline visit, when observations at the other baseline visit are available
- Missing values for one grader at a follow-up visit, when observations are available at the same follow-up visit from the other grader
- Missing values for both graders at a follow-up visit, when values other regions of interest from that eye are available at that visit
- Missing values for all regions of interest for a given eye at the follow-up visit

Complete case analyses will be included in reports. We will report multiple imputation results when we impute baseline visits based on other baseline visits. We will then report multiple imputation results when we extend to impute follow-up data for regions of interest when the second grader is imputed from the first. We will finally report multiple imputation results when we impute outcome data for regions of interest for which no follow-up data are available.

The latter is the primary outcome for the trial, and will be sharply distinguished from other analyses. We note that complete case analyses are biased.

Subsidiary analyses will be conducted to assess the role of image quality on missingness. Results may be biased because of treatment-related loss of image quality.

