3.1 Sample Size Planning

3.1.1 Alpha level

The study hypotheses are listed as bidirectional effects; we will never conduct one sided tests. All hypothesis tests proposed for the CNTF Implant Trial are two-sided.

Results will be judged significant using a two-tailed α of 0.05.

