3.1.2 Power

We plan recruitment of sufficient subjects for an 80% power to detect an effect size of 0.084 arcminutes over two years.

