3.1.4 Withdrawals and expected loss to follow-up

We conservatively allow for a 15% loss to follow-up based on prior studies.

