3.1.5 Sample size calculation methodology

We used a simplified version of the analysis we plan in order to estimate the power for the more complex analysis. This reduces the analysis to a paired T-test. More specifically, we determined the rate of change over time of the cone spacing in our pilot patients, and computed a pooled standard deviation over all these regions (in untreated persons) from which we derived an expected standard deviation of the difference in the total change in cone spacing after two years of approximately 0.11. Using the standard formula for the sample size of a one-sample T-test

(e.g. Chow et al, 2007, formula 3.1.2), we find we would need a total of 17 individuals per group, or 20 adjusting for loss to follow-up.

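### SAP 7.6.2 gives a missing-data method only for cone spacing and density, so the six Holm-tested secondary outcomes run on completers by default

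*SAP*

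**What the plan says.** - **Scope of the missing-data rule.** SAP 7.6.2 opens with "Missing values of cone spacing or density will be handled by regression-based multiple imputation in several steps". Its five steps are written in terms of graders, baseline visits, and regions of interest within an eye. It then remarks: "We note that complete case analyses are biased".
- **Expected loss.** SAP 3.1.4: "We conservatively allow for a 15% loss to follow-up based on prior studies". SAP 3.1.5 turns 17 evaluable participants into 20 enrolled.
- **Analysis of the secondary outcomes.** SAP 7.5.2.1 on acuity: "The template of §7.5.1.1 will be used here, except that we will simply model the difference in visual acuity between the eyes". It adds that regions and multiple graders do not apply. Sections 7.5.2.2 to 7.5.2.6 send the other five outcomes to the same template, directly or through the acuity section. The template in 7.5.1.1 has two times, baseline and final follow-up, and its primary test is placed at month 36.
- **Population.** SAP 4.1 makes all randomized patients the primary efficacy population.
- **Use of the results.** SAP 7.5.2: "the analytic results in this section are relevant both to safety (when results are worse in the treated eye), and to efficacy".
- **Data that may exist after withdrawal.** Protocol 5.6 asks people who withdraw to return for a safety visit that includes the month-30 assessments. Apart from ERG, the secondary measures are taken every six months (Protocol 4.1, SAP 2.3.2).

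**The concern.** The section headed as covering missing data and loss to follow-up cannot be applied to six of the outcomes that are formally tested. Its steps borrow from a second grader, the other baseline session or a neighbouring region, and these outcomes have no graders or regions to borrow from. Because the template needs a final value, someone who leaves early drops out of the test, whatever was recorded before.

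Two things are at stake. First, the tests would not be run on the population the SAP names, and any repair would be chosen after the data are seen. Second, if people leave because the implant eye has done badly, the completers look better than the randomized group, in tests the SAP says bear on safety as well as efficacy.

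**Working it through.** **1. The plan's own figure.** The inputs are "Results will be judged significant using a two-tailed α of 0.05" (SAP 3.1.1), "We plan recruitment of sufficient subjects for an 80% power to detect an effect size of 0.084 arcminutes over two years" (SAP 3.1.2), and "expected standard deviation of the difference in the total change in cone spacing after two years of approximately 0.11" (SAP 3.1.5).
- Standardized effect: 0.084 / 0.11 = 0.764.
- Normal approximation: ((1.96 + 0.84) / 0.764)² ≈ 13.5, so 14.
- Paired t-test (noncentral t): n = 16 gives 81.4% power and n = 17 gives 84.0%. The stated 17 is close and slightly generous.
- Dropout: 17 / 0.85 = 20. At the planning allowance, 0.15 × 20 = 3 participants (6 eyes) have no final score.

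**2. Can any 7.6.2 step score these outcomes?**

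| Step in SAP 7.6.2 | What it needs | Available for the six outcomes? |
|---|---|---|
| One grader missing, baseline or follow-up | a second grader | No (7.5.2.1) |
| Both graders missing at one baseline | the other baseline session | Does not address a missing final visit |
| Both graders missing at follow-up | other regions in that eye | No (7.5.2.1) |
| All regions missing at follow-up | a cone-measure imputation model | Not extended to other outcomes |

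The mixed model in SAP 7.5.1.3 could use partial follow-up. However, it is described as a complement, it is conditional on interim observations, and no secondary section cites it.

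**3. When does loss cause bias?** Both eyes leave together. If loss is unrelated to the treated-minus-sham difference, the completer mean is unbiased and only precision suffers. At the strictest Holm level, 0.05/6 = 0.0083, the effect detectable with 80% power (paired t-test) is 0.95 SD with 17 participants and 0.86 SD with 20. If loss is related to the difference, there is bias. For example, if 3 of 20 lose 0.3 logMAR in the implant eye, the others show no difference, and those 3 leave, the full-group mean loss is 3 × 0.3 / 20 = 0.045 logMAR and the completer mean is 0.

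**4. Size under stated assumptions.** None of the following comes from the documents:
- unit SD for the final between-eye change;
- correlation ρ of 0.5 to 0.8 between the last observed difference x and the final one;
- exactly 3 of 20 lost;
- an exact two-sided signed-rank test, standing in for the Wilcoxon test of SAP 7.5.1.1;
- in the moderate case, the odds of loss rise 2.7-fold per SD of worsening in x; in the extreme case, the three worst x values are lost.

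When loss depends only on x, the bias equals ρ times the mean of x among completers. That mean is about 0.14 (moderate) or 0.26 (extreme). So the bias is 0.5 × 0.14 = 0.07 to 0.8 × 0.14 = 0.11 SD, or 0.5 × 0.26 = 0.13 to 0.8 × 0.26 = 0.21 SD. Simulation with 100,000 runs per setting gave:

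| Loss | Bias toward implant | Per-test error at 0.05/6 | Power, true harm 0.72 SD, at 0.05/6 |
|---|---|---|---|
| Random | 0 | 0.8% | 48% |
| Moderate selection | 0.07–0.11 SD | 1.1–1.6% | 36–39% |
| Worst three lost | 0.13–0.21 SD | 1.8–4.4% | 30–34% |

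The random-loss error is below 0.83% because the exact signed-rank test with 17 pairs can attain only 0.79%. The 0.72 SD harm is the effect that 17 pairs detect with 80% power in an unadjusted 5% paired t-test.

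**5. Does using x help?** Regressing the final difference on x and averaging over all 20 gives bias of about 0 and a standard error of 0.23 to 0.25, against about 0.24 for completers. The zero bias follows from the set-up, since loss was made to depend only on x.

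**The case against.** - **The SAP never says it will use completers here.** That is so. Completer analysis is what the template does when no rule is given. The remark that such analyses are biased sits in a section on cone measures, next to a comment on image quality. A reader might infer that the SAP concedes bias in its secondary tests; it does not.
- **Harm would be seen elsewhere.** This largely stands. SAP 7.7 summarises adverse events leading to withdrawal and compares incidence between eyes. SAP 7.5.2.7 models event rates. SAP 6.2.3 has the SMC examine acuity and visual sensitivity for harm. SAP 7.5.2 itself says these tests cannot settle safety.
- **Lost participants are not without data.** Also right: Protocol 5.6 requests a visit and earlier visits exist. The gap is that the SAP does not say how to use them.
- **The wording may already allow interim visits.** SAP 7.5.2.1 tests whether the between-eye difference stays constant over time, and 7.5.2.6 lists months 12, 24 and 36 for ERG. Both could mean a longitudinal model, but both cite a template with only two times. That is an ambiguity to resolve, not a rule.
- **The 15% is a cautious planning allowance.** True. Loss could be smaller, or unrelated to the between-eye difference.

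**Conclusion.** The gap is real and no other section closes it. Six formally tested outcomes have no missing-data method. Read as written, they are analysed in about 17 of 20 participants instead of all randomized. This should be corrected before analysis, but it does not threaten the primary test.

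Under moderate selection the cost is 0.07 to 0.11 SD of bias toward the implant, a modest rise in per-test error (0.8% to 1.1–1.6%), and a loss of 9 to 12 percentage points of power to see a 0.72 SD harm. Losing exactly the three worst is an extreme case. All of this rests on the assumed SD, correlations, number lost and loss mechanism. Under random loss there is no bias.

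Two stronger readings are tempting and not supported. One is that dropout would hide harm in the trial as a whole: it would dilute harm in these six tests, while the adverse-event and SMC reviews remain. The other is that false-positive rates would run well above 5%. Such rates come from an unadjusted 5% test with the worst three lost, whereas the planned tests are Holm-corrected.

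**What to change.** Extend SAP 7.6.2 to the six secondary outcomes:

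1. Keep the final-visit treated-minus-sham change and the planned rank test. Multiply impute a missing final difference from that person's earlier between-eye differences and the withdrawal visit, in all randomized participants.
2. Reconcile 7.5.2.1 and 7.5.2.6 with the two-time template, so that it is clear which visits each test uses.
3. For ERG, reconcile the schedule first: SAP 7.5.2.6 uses month 36, while Protocol 4.1 schedules ERG at baseline, 12 and 24 months. As it stands, the final value could be missing for everyone. Then use the last scheduled ERG visit.
4. Report three analyses beside it: completers; a mixed model with a parsimonious covariance (an unstructured one for six follow-up visits has 6 × 7 / 2 = 21 parameters, for about 20 people); and a missing-not-at-random analysis that assumes worse implant-eye outcomes in those lost. Tabulate missingness by reason.

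The cost is SAP wording and a little programming, with no new visits. The price is a missing-at-random assumption. Imputation does not repair loss before month 6 or a late decline that nobody recorded, which is why the missing-not-at-random analysis is needed.

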7.6.3 Transformations and model adequacy

Because the legitimacy of the hypothesis test being conducted depends on the assumptions (i.e. normality and homoskedasticity for linear models, proportional hazards for Cox regression), the adequacy of the statistical model must be checked. Methods which will be employed will include (a) residual plots (vs. baseline value, vs. predicted values, and Q-Q plots), (b) jackknife influence estimates, and (c) tests for normality (including the Anderson-Darling and Shapiro-Wilk procedures).

7.6.4 Multiple comparisons

An alpha of 0.05 will be used for the primary efficacy analysis. For pre-specified secondary analyses, we will report both the P-value and the number of pre-specified analyses performed. Note that the results of secondary analyses are not independent events, making a Bonferroni correction very conservative.

7.7 Safety and tolerability

The analysis of safety in this study will include summaries of the following:

- Exposure
- Adverse events
- Adverse events and serious adverse events
- Adverse events leading to withdrawal
- Any deaths

The incidence of adverse events will be compared between treatment and sham eyes using the McNemar test.

Additional considerations are given in §7.4.

7.7.1 Exposure

Individual eyes are assumed to have exposure to the intervention assigned to the arm they were randomized to.

7.7.2 Adverse Events

7.7.2.1 Individual events

The proportion of subjects with at least one of the following safety-related events will be compared using Fisher's Exact Test. Non-serious adverse events (not requiring narrative form) are listed here: irritation or infection from dilation drops, bruising from blood work.

Serious ocular adverse events (which must be reported within 24 hours and which require a narrative form) are listed here: acute angle closure glaucoma precipitated by dilation, corneal abrasion after tonometry or electroretinography, risks associated with implantation surgery (cataract, retinal detachment, infection, bleeding).

In addition, we will compare the rate of each of the adverse events during the follow-up period using Poisson regression, which can take into account multiple instances of adverse events within a single subject.

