4.1 Outcomes

Primary Outcome:

The primary outcome is rate of change in cone spacing and rate of change in cone density as determined using AOSLO images of regions of interest (ROIs) preselected at baseline in eyes treated with CNTF compared to contralateral eyes treated with sham surgery over 30 months. Cone spacing and density will be measured by 3 independent graders who will remain fully masked to the treatment assignment throughout the duration of the trial. We will compare rates of change in cone spacing and cone density between CNTF-treated and contralateral sham-treated eyes through 30-months using pooled linear regression.

Secondary Outcomes:

Secondary outcome measures will involve comparing rates of change in standardized measures of visual function between CNTF- and sham-treated eyes. Secondary outcomes will include the following functional and structural assessments: mean and median change in best spectacle-corrected visual acuity (BCVA) using the ETDRS protocol, changes in visual field sensitivity and foveal sensitivity in decibels (dB) using automated static perimetry using the Humphrey visual field 10-2 protocol and rod and cone-mediated fundus-guided microperimetry using a modified Nidek MP1, changes in thickness of the outer nuclear layer (ONL) and outer segment plus RPE (OS+) layer thickness as measured using spectral-domain optical coherence tomography (SD-OCT), and changes in full-field ERG scotopic and photopic standard a- and b-wave amplitudes and timing from baseline to 36 months. All parameters except full-field ERG will be measured at 6, 12, 18, 24, 30 and 36 months after implant surgery; standard full-field ERG will be performed according to ISCEV standards at baseline, 12, and 24 months.

Safety Outcomes:

Safety of the NT-501 ECT technology implant has been demonstrated in prior Phase 1 and Phase 2 trials of the implant. Separately from efficacy outcomes which demonstrate a reduction or increase in function, safety parameters will continue to be collected and assessed by the following outcomes (occurrence of these outcomes does not necessarily require explant):

- Rejection or extrusion of the NT-501 device.
- Protocol-related abnormal findings from serum chemistry, hematology, and urinalysis (those abnormal findings that are determined to be clinically significant by the Principal Investigator).

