- Peri-implant fibrosis, which either blocks the visual axis of the implanted eye or affects the lens or retina (minor/moderate fibrosis around the implant and/or the attachment point is an expected possibility and will be considered safe on ocular function). Attention should focus on fibrosis that may detach the retina.
- Development of choroidal neovascularization (CNV) in the implanted eye, in which case it may be considered a safety event and explant will be considered.

- Adverse events affecting ocular function, which are different from those expected in the normal course of RP or Usher Syndrome, which are thought to be potentially related to the implant.
- Local or systemic toxicities considered serious adverse events that are potentially related to the implant.

There are risks associated with the surgeries to implant and explant the device and with the sham surgery. In general, the risks of intra-ocular surgery are very small. Some side effects could occur locally in the eye and could affect the participant's vision. There may be pain or infection, a small amount of bleeding, cataract, vitritis, and/or mild astigmatism. A retinal detachment could also possibly occur. Participants may experience a transient red eye from superficial bleeding and itching or a foreign body sensation in the corner of the eye from irritation of the suture itself. These side effects are usually temporary and generally clear up in two weeks or less. In many cases, topical antibiotics and topical steroids can treat minor degrees of inflammation or infection. More serious infection or inflammation may require further surgery on the eye, likely with removal of the implant.

In addition, all adverse events will be collected regardless of severity or potential relationship to the implant, CNTF, or surgical procedure.

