- Once the implant has been removed the sclerotomy will be closed with 7-0 vicryl suture and the retina inspected for tears or bleeding using indirect ophthalmoscopy.
- The conjunctiva will be closed.

4.7 *Examination Requirements*

At scheduled visits, participants will undergo a medical evaluation and an ophthalmic examination, which includes eye photography and vision measurements and laboratory tests. Scheduled visits are approximated with windows as defined in section 4.4.1 Study/Follow-up Visit and Assessment Schedule.

The following are examinations to be performed at the times indicated in section 4.4.1.

1. Medical evaluation including:

- Demographic data
- Medical history, including confirmation of RP diagnosis
- Vital signs (blood pressure, respiration, and temperature)
- Brief physical examination with body system review
- Herpes zoster history
- Adverse Event assessment
- ECG (once prior to surgery)

2. Complete ophthalmic examination including:

- Slit Lamp Exam including AREDS Clinical Lens Grading²
- Implant site clinical examination
- Ophthalmoscopic Exam
- Manifest refraction
- BCVA (using the ETDRS methods for refraction and EVA)
- IOP
- Humphrey 10-2 Visual Field Testing
- Dark Adapted Fundus Guided Micropertimetry using red and blue targets at 2 degree intervals across a horizontal line extending 10 degrees with a Goldmann V, 200 ms target using a 4-2-1 threshold strategy to assess rod and cone-mediated function

² The AREDS clinical lens grading protocol will be used for protocol scoring purposes (using slit lamp without any photographs).

- Full Field ERG using ISCEV standard protocol (Marmor et al, 2009)

3. Photography and measurements including:

- Axial length, corneal curvature, anterior chamber depth measures using the IOL master (Carl Zeiss Meditech, Inc.)

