6.3 Efficacy and Safety Variables

The primary efficacy variable is the rate of change in cone spacing and cone density from baseline to 24 months. Secondary efficacy variables will include: mean change from baseline value in Humphrey Visual Field Sensitivity (VFS) from baseline to 24 months, mean change in “5-point” VFS from baseline to month 24 (using the 5 retinal points with greatest average change), mean change from baseline in Best Corrected Visual Acuity (BCVA) at 12, 18, and 24 months, and changes in ERG, Optical Coherence Tomography (OCT), clinical grades of

inflammation (anterior chamber cell and vitreous haze grades), and vision-related quality of life (NEI-VFQ25) at each visit.

The mean change in VFS will be calculated using the sum of all points at baseline and each follow-up visit. Likewise, the 5 points with greatest change from baseline will be selected for each patient based on the average score per point across replicates at baseline and at month 24; the mean of these 5 points will be used to compute the change from baseline in “5-point” VFS.

Safety variables will include the incidence of adverse events, changes in vital signs, marked changes in clinical laboratory data, ECG abnormalities, and findings during physical examinations.

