6.2.2 Meetings

All teleconference meetings of the SMC and study personnel will consist of (a) “open” sessions, which may be attended as needed by masked study personnel, and (b) “closed” sessions, which may only be attended by unmasked study personnel (TP). Care will be taken so that *no* treatment assignments, data which would allow treatment assignments to be determined, or outcome data based on treatment assignments will be revealed during the open sessions.

Interim reports for the SMC will be prepared by study biostatistician (TP). These reports will include (a) recruitment overall, and by study site, (b) compliance, and (c) retention. The reports will also list study outcomes, and all adverse outcomes, including mortality and perforations. The SMC will determine the database closure dates for each report in advance; archival copies of the (a) main SQL database, and (b) study analysis file as they exist at the time of each report will be maintained. All reports will be sent using secure email to the members of the SMC two weeks prior

to each meeting. Each interim report will be labeled clearly as confidential, printed in binding so that the contents are not visible from the outside, and labeled with the name of each person authorized to receive it. In addition, redacted versions of the interim reports will be prepared which contain no masked study information, and which are suitable for restricted distribution to other personnel on an as-needed basis. All hard copies will be destroyed at the end of each meeting, except for a copy to be kept in a locked file cabinet accessible only to TP.

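### The SAP names no analysis for device rejection or extrusion, peri-implant fibrosis or CNV, gives none for laboratory, vital-sign or physical-examination safety variables, and the 36-month ECG variable has no follow-up ECG

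*SAP*

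**What the plan says.** Protocol 4.1 lists six safety outcomes. Four are specific:

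- "Rejection or extrusion of the NT-501 device"
- "Protocol-related abnormal findings from serum chemistry, hematology, and urinalysis", where the investigator judges them clinically significant
- "Peri-implant fibrosis, which either blocks the visual axis of the implanted eye or affects the lens or retina"
- "Development of choroidal neovascularization (CNV) in the implanted eye"

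The other two are generic: ocular-function events outside the usual disease course and possibly due to the implant, and serious toxicities possibly related to it. Protocol 4.1 also mentions vitritis among the surgical risks.

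Protocol 6.3 names adverse-event incidence and four further safety variables: "changes in vital signs, marked changes in clinical laboratory data, ECG abnormalities, and findings during physical examinations". The Protocol Summary lists the same variables with a horizon of 36 months. On ECG, Protocol 4.7 says "ECG (once prior to surgery", and Table 1 shows it only at Baseline 3. Protocol 4.6.1 adds monitoring during the operation.

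SAP 7.7.2.1 takes a list of events and compares the proportion of subjects with each by Fisher's exact test, with Poisson regression for rates. The non-serious entries are: "Non-serious adverse events (not requiring narrative form) are listed here: irritation or infection from dilation drops, bruising from blood work". The serious ocular entries are angle closure after dilation, corneal abrasion, and four surgical risks (cataract, retinal detachment, infection, bleeding). SAP 7.7 summarises exposure, adverse events, serious events, withdrawals due to events, and deaths, and compares adverse-event incidence between eyes by McNemar's test. SAP 7.7.2.2 adds four pooled ocular and non-ocular categories. For the committee, SAP 6.2.2 says: "The reports will also list study outcomes, and all adverse outcomes, including mortality and perforations".

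**The concern.** SAP 2.1 gives safety of the implant as one of the trial's two questions. The Protocol says which events matter for this device, but the event-level analysis in the SAP is built on a list that leaves out the three most specific to it. A pooled ocular total places an extrusion beside any other ocular event and does not say how many implants failed. The report might still describe such events, but nothing fixes in advance how they are counted, on what denominator, or with what interval. Several safety variables stated in the Protocol would also reach the report with no planned table.

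**Working it through.** No stated figure is in dispute, so the check sets the texts side by side and then asks what a named analysis would give.

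**1. Protocol 4.1 outcomes against the SAP**

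| Protocol 4.1 outcome | Named in SAP 7.7.2.1? | Where it is otherwise counted |
|---|---|---|
| Rejection or extrusion | No | General AE summaries, McNemar, pooled ocular totals, if recorded as an AE |
| Peri-implant fibrosis as defined | No | Same |
| CNV | No | Same |
| Clinically significant laboratory findings | No | AE totals, because Protocol 5.5 makes them AEs; no laboratory table |
| Ocular-function events beyond disease course | Generic | Pooled ocular categories, without the relatedness qualifier |
| Serious implant-related toxicity | Generic | Pooled serious categories, without the relatedness qualifier |

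Three outcomes are specific and unnamed, a fourth has only AE-level coverage, and two are covered by pooling. Vitritis is also absent from the list.

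**2. Protocol 6.3 variables against SAP 7.7**

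Adverse events are analysed. Vital signs, laboratory data, ECG and physical findings are not: 4 of 5 have no analysis. SAP 2.3.1 says laboratory measurements will contribute to the safety assessment and sends the reader to 7.4, which contains no laboratory analysis. SAP 7.1.3 tabulates laboratory measurements at baseline only.

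**3. ECG**

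The Summary's horizon is 36 months. The schedule has one pre-operative ECG plus monitoring in theatre, so follow-up ECG recordings number zero.

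**4. Device-only events**

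The sham eye receives no device (Protocol 4.6.1), so rejection, extrusion and peri-implant fibrosis cannot occur there. The natural summary is n/N of implanted eyes with an exact interval. With zero events the two-sided 95% upper limit is 1 − 0.025^(1/n). The documents give three sizes, so all are shown:

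- n = 10 (minimum in Protocol 6.1): 1 − 0.025^(1/10) = 30.8%
- n = 20 (SAP 3.1.5): 1 − 0.025^(1/20) = 16.8%
- n = 30 (Protocol section 4): 1 − 0.025^(1/30) = 11.6%

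If the true rate were 5% (an assumption), the chance of at least one event is 1 − 0.95^n: 40%, 64% and 79%.

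**5. Events possible in either eye**

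Each participant supplies one implanted and one sham eye. Fisher's test treats the eyes as independent; McNemar's test uses the discordant pairs. Take n = 20, five implanted eyes affected and no sham eye. Fisher gives p = 0.047. Exact McNemar gives 2 × 0.5^5 = 0.0625, and needs six discordant pairs in one direction (2 × 0.5^6 = 0.031). The choice of test can change the reading, and SAP 7.7 already uses the paired one.

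**The case against.** The strongest reply is that nothing is lost. Protocol 4.1 and 5.2 require every adverse event to be collected. SAP 7.7 summarises and compares adverse events without limiting them to the list, SAP 7.5.2.7 models their rate, and SAP 7.7.2.2 pools them. An extrusion would be recorded and would be visible to anyone reading the adverse-event summary. The Poisson sentence in 7.7.2.1 could even be read as covering every type of event. The interval widths above reflect the size of the trial, not a fault in the SAP.

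Most of this stands, and it limits the point. It does not supply a named, prespecified analysis of the device outcomes. A Poisson comparison with sham says little about an event that sham eyes cannot have. It also does not supply the missing laboratory, vital-sign and physical-examination tables.

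A reader might infer more than the documents support:

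- **That no Protocol safety outcome is analysed.** The two generic outcomes fall within the pooled categories, and clinically significant laboratory findings count as adverse events.
- **That only dilation and blood-draw effects are compared.** The list also has cataract, detachment, infection and bleeding.
- **That the safety committee would not see device events.** SAP 6.2.2 covers all adverse outcomes, and SAP 6.2.3 sends serious events to the committee chair within 24 hours.
- **That fibrosis goes uncounted because minor or moderate fibrosis is expected.** Such fibrosis lies outside the outcome as Protocol 4.1 defines it.
- **That the word perforations was carried over from the corneal-ulcer trial's SAP in the reference list.** It is not among the Protocol's safety outcomes, but its origin cannot be shown.

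**Conclusion.** The point holds as a gap in prespecification, not in data collection or committee oversight. Rejection or extrusion, defined peri-implant fibrosis and CNV have no analysis by name. Four of the five Protocol 6.3 safety variables have none in SAP 7.7, and for ECG the 36-month wording cannot be met from the schedule. Fisher's test in 7.7.2.1 does not fit the paired-eye design. The size is modest but worth correcting: an implanted-eye incidence with its exact interval (upper limit 30.8%, 16.8% or 11.6% if no events occur) is the informative summary for device-only events, and no section specifies it. Those limits assume one implanted eye per participant, all followed, at the three sample sizes the documents give.

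**What to change.** Keep the existing entries in SAP 7.7.2.1 and add to them:

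1. **Device-only events** (rejection or extrusion, peri-implant fibrosis as defined in Protocol 4.1, explant): n/N of implanted eyes with an exact 95% confidence interval and no sham comparison.
2. **Events possible in either eye:** add CNV and vitritis, and analyse them with cataract, detachment, infection and bleeding by a paired implant-versus-sham comparison in place of Fisher's test.
3. **Participant-level variables:** change from baseline in laboratory values and vital signs, and a summary of physical findings. Point the SAP 2.3.1 cross-reference to this section.

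Tables of IOP, lens grade and cell or haze grade are optional.

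In SAP 6.2.2, name the device outcomes as examples in place of perforations; the scope of the report does not change.

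Reconcile the ECG safety variable in the Protocol Summary and 6.3 with Table 1 and 4.7. One option that needs only wording is to describe it as pre-operative and intra-operative; the choice is the sponsor's.

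The cost is SAP and Protocol wording and a few tables. Implant-site examination, vital signs and brief physical examination are scheduled throughout follow-up, laboratory tests are repeated during it, and all adverse events are collected, so no new data are needed.
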